## Osteoporotic fracture

Fracture site	ICD10	ICD9CM	READ	ICPC
			XA0FK, XaB0o, XE1pj, S3zz., TC7..	L76
Unspecific	M80		N3303, N3315, N3316, N331B, NyuB0, NyuB8	
Clavicle	S42.0	810	S20..., S20z.	
Scapula	S42.1	811	S21..., S21z.	
Humerus	S42.2, S42.3, S42.4	812	S22..., S22z., XA0GS, XA0GT, XA0GQ	
Radius/Ulna	S52	813	S230., S2317, S2318, S2319, S2323, S234C, S234D, S234E, S2333, S2356, S235C, S235D, S235E, S23x., S23y., S23z., XE1ks, XA0GX, XA0Ga, XA0Gb, XA0Gl, XA0GV, XA0GW, XA85j, XM16p, XE1ee, XE1kw, XE1kv, XE1ky, XE1kz, 7K1LL	L72
Carpal bone/s	S62.0, S62.1	814	S24..., S4C0y, S4C1y, S4C2y, S4C3y, XA0E4, XA0ES	
Metacarpal bone/s	S62.2, S62.3, S62.4	815	S25..., Xa3he, XA0Gq, XA0Gr	
Arm/upper limb (unspecific)		818		
Hand (unspecific)				L74
Spine	S12, S22.0, S22.1, S32.0, S32.7, S32.8, T08	805	S10z., XE1kW, XE1pT, S10B., XA0G8, Syu34, XA0GB, XA0GM, XA0GN, XE0ln, 7J42z, 7J41., 7J43y, 7J43z, XE0lo, XA0Ds, XA0Dt, XA0Dv, XA0Dw, S10x., S10y., XE1kX, S10A2, XM1JV, XE1kf, Xa1u3, S114., S115., 7J420, 7J42y, 7J421, 7J423, 7J424, 7J425, XE1kn, S11z., XM1JU, N3318, N3319, N331A	
Rib/s/Sternum	S22.2, S22.3, S22.4, S22.5	807.0 to 807.4	XA0Gv, XA0Gw, XA0Gy, XA0Gz, S120., S121., S122., S123., S4J00, S4J10, S4J20, S4J30	
Pelvis	S32.1 to S32.5, S32.8	808	XA0H0, Xa3hd, S10B., S13., Syu34, S4J01, S4J11, S4J21, S4J31, S108., S109.	

Hip/Proximal femur	S72.0, S72.1		820	XaBDT, XaBDU, XaEJD, XA0HE, XA0HF,XA0HG, XA0HH, XA0HI, XA0HK, XA0HL, XE114, XE115, XE116, XE117, XE118, XE119, XM1Ne, XM1Nf, XM1Ng, XM1Nh, XM1Ni, XM1Nj, 7K1L4, X601I, X601L, X601M, X601N, X601P, X601S, X601T, X601U, XaEJD, S30w., S30x., S30z., S300., S301., S302., S303., S3003, S3004, S3014, S304.	L75
Femur (others/unspecific)	S72.2 to S72.9		821	XA0HC, XA0HD, XA0HJ, XA0HN, XA0HO, XA0HP, XA0HQ, XA0HR, XE11A, XE2ru, XE2rv, S31., S31z., S3101, S3111, S312x, S312z, S3120, S3122, S3132, S313z, S3130, 7K1L5	L75
Patella	S82.0		822	S32z., S32., XaCln	
Tibia/Fibula	S82.1 to S82.4		823	S33z., S33., Xa0m8, Xa85k, XA0HT, XA0HU, XE11B, XE11C, XE11D, XM00Y, XM16s, 7K1L7	L73
Ankle	S82.5, S82.6, S82.8		824	S34., S4G1., 7K1L8, 7K1E4, XA0Ee, XA0EG, XA0Hh, S4G., Xa1n1, Xa1mv, Xa1mz	
Tarsal/metatarsal bone/s	S92.0 to S92.3		825	Syu94, XA0Hi, XE11H, S353., XE11F, S35z., S3520, S3530, S352z, S353z	
Foot (unspecific)					L74

*Not considered as osteoporotic fractures: skull, face, jaw, coccyx, phalanx (fingers and toes), ankle and cervical spine*

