## 6. MILESTONES

Milestone	Planned date
Protocol submission to EMA	by 30 June 2014
Protocol approval by EMA	March 2015 *
Contract signature for study roll-out phase	April 2015*
Registration in the EU PAS register	April 2015*
Start of data collection	April 2015*
Statistical Analysis Plan	May 2015
End of data collection	End of June 2015
PSUR Update 1	October 2015
Start of data collection (second wave)	April 2016
End of data collection (second wave)	End of June 2016
PSUR Update 2	October 2016
Start of data collection (third wave)	April 2017
End of data collection (third wave)	End of June 2017
PSUR Update 3	October 2017
Final report of study results	End of November 2017

*\*Delay will impact the subsequent dates*

Milestones have been planned to maximise the efficiency and availability of data retrieval from the different data sources. A summary of such information is provided here:

Data source (Country)	Periodicity of updates	Time of the year when updates are released	Data availability for each update
SIDIAP (Spain)	Yearly	April-May	End (December 31 st ) of previous calendar year
IPCI (NL)	Yearly (twice is possible)	April-May	Variable as GPs provide not all at same time
THIN (UK)	Three times per year	Irregular	Variable as GPs provide not all at same time
HSD (Italy)	Every 6 months	June and December	End of previous calendar year (in June); up to June in December.
AUH (Denmark)	Yearly	May	December 31st the previous year

Both national regulations and prescribing practices have changed throughout the participating databases in recent months. As a consequence, in Italy, where GPs in primary care are not allowed anymore to initiate or renew strontium ranelate treatment since December 2013, the number of incident strontium ranelate users in the assessment period is expected to be null or very low. This point will be assessed for the first PSUR update (October 2015) as part of the analyses of the utilization patterns at population level (see [section 9.7.2.1](#)).

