  - High absolute fracture risk, defined as  $\geq 10\%$  5-year fracture risk according to the Garvan prediction tool (Nguyen, 2008) (where data on age and either bone mineral density or weight are available for the estimation of risk).

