#### **9.4.2. HSD – CSD Longitudinal Patient Database**

The Italian partner for the study will use the Health Search CSD Longitudinal Patient Database (HSD), a longitudinal observational database that is representative of the Italian general population. HSD was established in 1998 by the Italian College of General Practitioners (Filippi, 2005). The HSD contains data from computer-based patient records from a selected group of GPs covering a total of 1.5 million patients) located throughout Italy. These GPs voluntarily agreed to collect data for the database and attend specified training courses. The database includes information on the age, gender, and identification of the patient, and GP registration information, which is linked to prescription information, clinical events and diagnoses, hospital admission, and causes of death. All diagnoses are coded according to ICD-9-CM. Drug names are coded according to the ATC classification system (WHO, 2008). To be included in the study, GPs must have provided data for at least 1 year

and meet standard quality criteria pertaining to: levels of coding, prevalence of well-known diseases, and mortality rates (Cricelli, 2003). The HSD has been used as data source for a number of peer-reviewed publications on the prevalence of disease conditions, drug safety and prescription patterns in Italian primary care (Cazzola, 2011). Approval for use of data is obtained from the Italian College of General Practitioners for each study.

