### ***New restrictions***

Prevalence of each of the new restrictions for indication will be estimated on a patient level (new and prevalent users of SR) by age, sex, period and country. 95% Confidence Intervals will be estimated using a binomial distribution.

Interrupted time series analyses with segmented linear regression will be carried out to assess the impact of the RMM on these, as described above. Primary outcomes of interest will be proportion of SR users with: 1. A history of previous osteoporotic fracture/s or a “high estimated fracture risk” (as defined above); 2. Therapy initiation by a physician experienced in the treatment of osteoporosis (as defined above). 3. SR use not in first line (as defined above).

These analyses will be conducted separately for prevalent and incident SR users.

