### 9.7.4. Pooling

All estimates will be calculated by databases and pooled according to a meta-analysis approach (random or fixed effects model). In addition, to optimize power, we will conduct a mega-pooled analysis, that will estimate the effects putting all individual level data together (fixed and random effects will be checked).

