#### Myocardial infarction / angina pectoris / aorto-coronary bypass surgery

Terms	ICD10 (SIDIAP, Aarhus hospital outpatients)	ICD9CM (HS, Aarhus hospital admissions)	Read Codes (THIN UK)	ICPC (IPCI)
Cardiac infarction	I22 I21			
MI - Myocardial infarction			X200E	
Acute myocardial infarction	I21		G30.. XE0Uh	K75
Acute myocardial infarction, unspecified	I21.9	410.9		
Myocardial infarction (acute) NOS	I21.3	410		
Acute myocardial infarction, unspecified site, episode of care unspecified		410.90		
AMI NOS, unspecified		410.90		
Acute myocardial infarction, subendocardial infarction		410.7	G32..	
Old myocardial infarction*	I25.2	412		
Healed myocardial infarction*			XE2aA G32.11	
Old myocardial infarction*			XE2aA	
Subsequent/recurrent myocardial infarction	I22		G35..	
Subsequent myocardial infarction of unspecified site	I22.9		Gyu36	
Subsequent myocardial infarction of other sites	I22.8		Gyu35 G353.	
Subsequent myocardial infarction of anterior wall	I22.0		G350. GYU3600	
Subsequent myocardial infarction of inferior wall	I22.1		G351.]	
Subsequent acute subendocardial myocardial infarction	I22.2			
Subsequent nontransmural myocardial infarction NOS	I22.2			
Subsequent myocardial infarction (acute) NOS	I22.9			
Reinfarction of myocardium			G35..	
Acute subendocardial myocardial infarction	I21.4		G307.00	
Acute myocardial infarction, subendocardial infarction, episode of care unspecified		410.70		

Terms	ICD10 (SIDIAP, Aarhus hospital outpatients)	ICD9CM (HS, Aarhus hospital admissions)	Read Codes (THIN UK)	ICPC (IPCI)
Nontransmural myocardial infarction	I21.4			
Acute myocardial infarction, of anterolateral wall		410.0	G300.	
Acute anteroseptal myocardial infarction			G3011	
Acute inferior myocardial infarction		410.4	X200K	
Acute myocardial infarction, true posterior wall infarction		410.6		
True posterior myocardial infarction			G306.	
Acute myocardial infarction, of inferoposterior wall		410.3	G303.]	
Other specified anterior myocardial infarction			G301.]	
Acute transmural myocardial infarction of unspecified site	I21.3		Gyu34	
Acute transmural myocardial infarction of anterior wall	I21.0 122.0			
Acute transmural myocardial infarction of inferior wall	I21.1 I21.11 I21.19 122.1			
Acute transmural myocardial infarction of other sites	I21.2 I21.21 I21.29 122.8			
ECG: old myocardial infarction*			3232.	
Anterior myocard.infarct NOS		410.8	G301z	
Other acute myocardial infarct			G30y.	
Other acute myocardial inf.NOS			G30yz	

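### The osteoporotic-fracture code list has no ICD-9-CM code for the generic osteoporotic-fracture diagnosis, so Italy's fracture level is not comparable with other countries' and a pooled period share can shift when Italy drops out

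*Protocol*

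**What the plan says.** The code list for osteoporotic fracture in Appendix 14.3.2 has parallel columns for ICD-10, ICD-9-CM, READ and ICPC. The Unspecific row carries M80 in ICD-10 and "N3303, N3315, N3316, N331B, NyuB0, NyuB8" in READ, with nothing in ICD-9-CM. The Spine row adds N3318, N3319 and N331A in READ, against 805 alone in ICD-9-CM. Every ICD-9-CM entry in the table belongs to an anatomical site: 805, 807.0 to 807.4, 808, 810 to 815, 818 and 820 to 825.

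Section 9.4.2 says of HSD: "All diagnoses are coded according to ICD-9-CM".

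The list feeds the definition of severe osteoporosis in Section 9.3.2 and the first primary outcome under New restrictions in Section 9.7.2.2, whose first limb is "A history of previous osteoporotic fracture/s". The second limb is a Garvan 5-year fracture risk of at least 10%, usable only "where data on age and either bone mineral density or weight are available for the estimation of risk".

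Section 6 reports that Italian GPs have been unable to initiate or renew strontium ranelate since December 2013, and that "the number of incident strontium ranelate users in the assessment period is expected to be null or very low". Section 9.7.4 pools database-level estimates by meta-analysis and adds: "we will conduct a mega-pooled analysis". The only country exclusion named in Section 9.7.5 is Spain.

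**The concern.** The same clinical history is classified differently depending on the coding system. Three things follow.

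- Italy's recorded share of users with a previous osteoporotic fracture is lower than it would be under the ICD-10 or READ list. Italy's own level is therefore understated.
- Levels cannot be compared cleanly across member states, although Section 8 asks about effectiveness in different member states.
- Italy is a large part of the reference period and is expected to be nearly absent from the assessment period. A pooled share built from whichever databases have users in each period can then change because the mix changes, with no change in prescribing. If Italy under-records and then leaves, the movement is towards apparent success of the risk minimisation measures.

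**Working it through.** **The plan's own yardstick.** Section 9.5.1 sizes the indication outcomes for ±5 points at 95% confidence. With p = 53.1%: n = 1.96² × 0.531 × 0.469 / 0.05² = 382.7, rounded up to 383, as stated. Five points is therefore a fair reference for judging a shift.

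**Is the blank cell real?** The extracted columns shift from the Hip row onward, but the Unspecific and Spine rows come earlier and align. No other row supplies a generic ICD-9-CM fracture code.

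**Inputs.**
- Italy's weight w, from Table (9.5) 1 for 2012: incident 1,209/5,819 = 20.8%; prevalent 10,129/27,764 = 36.5%. The Italian prevalent counts by sex add to 613 + 9,616 = 10,229 and the totals by sex to 1,841 + 26,013 = 27,854. Using those gives 36.7%, so this discrepancy does not matter here.
- Range for previous fragility fracture, from Section 9.5.1: 13.0% to 53.1%. I use p = 40% as an illustration inside it.
- Missed fraction m, meaning the share of Italian qualifying patients whom only the absent code would find: **not in the documents**. Assumed range 5% to 50%.

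**Formula.** With the same true share p everywhere, the pooled share is p(1 − w·m) with Italy and p without it. The artificial rise when Italy leaves is p·w·m.

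| m | Incident, p = 40% | Prevalent, p = 40% |
|---|---|---|
| 5% | 0.4 points | 0.7 points |
| 10% | 0.8 | 1.5 |
| 25% | 2.1 | 3.6 |
| 50% | 4.2 | 7.3 |

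Example: 0.40 × 0.208 × 0.50 = 4.2 points.

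Across the same range of m, p = 13.0% gives 0.14 to 1.35 points (incident) and 0.24 to 2.37 (prevalent). At p = 53.1% the shift is 0.55 to 5.5 and 0.97 to 9.7 points. There it reaches 5 points when m = 0.05/(0.531 × 0.208) ≈ 45% (incident) or 0.05/(0.531 × 0.365) ≈ 26% (prevalent).

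**Spain excluded.** Italy's weight becomes 1,209/(5,819 − 4,008) = 66.8% (incident) or 10,129/(27,764 − 14,502) = 76.4% (prevalent). The planned sensitivity analysis would therefore enlarge a pooled artefact: at p = 53.1% and m = 30% it is 10.6 or 12.2 points.

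**Direction.** If Italy's true share is pI and the others' is p, the change on Italy's exit is w[p − pI(1 − m)]. It is negative when pI/p exceeds 1/(1 − m), which is 1.11 at m = 10% and 1.43 at m = 30%. With pI = 53.1%, p = 40% and m = 10%, the pooled share falls by 1.6 points (incident) or 2.8 (prevalent).

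**Scope beyond Italy.** The header of the myocardial infarction list reads "ICD9CM (HS, Aarhus hospital admissions", whereas Table (9.4) 1 gives ICD-10 for Aarhus. If the header is right, Aarhus admissions share the gap, but Aarhus holds only 46 of 5,819 incident users.

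**The case against.** The strongest reply is that a blank cell shows unequal lists, not a measured deficit. Any Italian fracture also entered under a site code is found, and a patient can qualify on estimated risk instead. This stands, and it is why m is unknown and may be small.

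Second, the main analysis is an interrupted time series run in each data source, each acting as its own control (Section 9.7.2.2). A constant gap scales Italy's series down but creates no step at the intervention, and a database without assessment-period users contributes no estimate of change to a meta-analysis. This also stands. The exposure is confined to Italy's level, between-country comparisons, and pooled period shares that are crude or come from a mega-pooled model ignoring database. Section 9.7.4 says fixed and random effects will be checked there, which may help.

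Third, the code lists are provisional: they are to be discussed with partners before extraction, the new-indication proxies are to be refined, and database-specific rates are to be benchmarked. This is partly persuasive. None of those steps flags this cell, and benchmarking that looks for outliers may not notice a partial under-count among genuine country differences.

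A reader might infer more: that Italy under-counts substantially, that the pooled share must rise, or that the safety odds ratios are biased by the gap. The documents do not support these. They give no missed fraction, the sign depends on Italy's true share, and controls are matched to cases within data source (Section 9.3.1), so coding differences between databases do not enter that contrast.

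**Conclusion.** The gap is real and specific. As written, the list can find fewer fracture histories in HSD than in SIDIAP or THIN for one limb of a named primary outcome, and Italy's level is not comparable with theirs. The effect on a crude or mega-pooled before/after share runs from negligible to larger than the plan's 5-point precision. It rests on three assumptions: 2012 weights standing for a reference period that ends in May 2013, equal true shares across countries, and a missed fraction the documents do not give. The figures also apply m to the whole severe share; the estimated-risk limb would recover some patients, which is the same as a smaller m. The within-database time series is largely unaffected. The correction is worth making because it is cheap before extraction, not because a large bias has been shown.

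**What to change.** 1. Before extraction, have the HSD partner fill the ICD-9-CM cell of the Unspecific row with the equivalent pathological or osteoporotic fracture codes, or record why none is used. The same check applies to the Spine row. The documents do not name the codes; 733.1x is a candidate for the partner to confirm.
2. Report fracture counts by list row and database, so that an empty row is visible before analysis.
3. Show any pooled before/after share for severe osteoporosis a second time, restricted to databases with users in both periods.

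The cost is one code-list edit, one count table and one extra pooled run. The downside is that a few pathological fractures of other cause may be counted in HSD.

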### All-cause death

Terms	ICD10	ICD9CM	Read Codes	ICPC
Dead Died Death Has died			XM01Y XE1hB	A96
Dead NOS			22JZ.	
Instantaneous death	R96.0	798.1	R211. XM1AY Ua1q3	
Unattended death	R98	798.9	R213.	
Unattended death NOS			R213z	
Sudden cardiac death, so described	I46.1		G5751	
Other sudden death, cause unknown	R96	798	RyuC1 R21.. R21z. XM1Ac	
Death occurring less than 24 hours from onset of symptoms, not otherwise explained	R96.1	798.2	R212. R212z	

In the IPCI database, cause of death based on ICD/ICPC/READ codes [if recorded, or in free text.](#)

### Hypertension only if uncontrolled

Terms	ICD10	ICD9CM	Read Codes	ICPC
Hypertension	I10 I11 I12 I13 I15	401* 402* 403* 404* 405* 362.11 437.2	6627.00	K86 K87
			6628.00	
			6629.00	
			14A2.00	
			38DE.00	
			662b.00	
			662c.00	
			662d.00	
			662F.00	
			662G.00	
			662H.00	
			662O.00	
			662P000	
			662q.00	
			662r.00	
			67H8.00	
			7Q01.00	
			7Q01y00	
			8B26.00	
			8BL0.00	
8CR4.00				
8I3N.00				
F421300				
G2...00				
G2...11				
G20..00				
G200.00				
G201.00				
G202.00				

Terms	ICD10	ICD9CM	Read Codes	ICPC
			G203.00	
			G20z.00	
			G20z.11	
			G21..00	
			G210.00	
			G210000	
			G210100	
			G211.00	
			G211000	
			G211100	
			G21z.00	
			G21z000	
			G21z011	
			G21z100	
			G21zz00	
			G22..00	
			G220.00	
			G221.00	
			G222.00	
			G22z.00	
			G22z.11	
			G23..00	
			G230.00	
			G231.00	
			G232.00	
			G233.00	
			G23z.00	
			G24..00	
			G240.00	
			G240000	
			G240z00	
			G241.00	
			G241000	
			G241z00	
			G244.00	
			G24z.00	
			G24z000	
			G24zz00	
			G2y..00	
			G2z..00	
			G672.00	
			Gyu2.00	
			Gyu2000	
			Gyu2100	
			L122.00	
			L122000	
			L122100	
			L122300	
			L122z00	
			L127z00	
			L128.00	
			L128200	
			Lyu1.00	

### Precautionary conditions

Terms	ICD10	ICD9CM	Read Codes	ICPC
Type 2 diabetes mellitus	E11	250 (except 250.*1 and 250.*2) 271.4 357.2 366.41	C10.. C101. F4640 G73y0 X00Ag X305t X30kk X40J5 Xa0IK XE11P XE15k XE2Ne	T88 T90
Hyperlipidaemia			44P3.00 44P4.00 C320.00 C320.11 C320.12 C320.13 C320000 C320100 C320200 C320300 C320400 C320500 C320y00 C320z00 C321000 C321.00 C321.11 C321.12 C322.00 C322.11 C322.12 C322.13 C322000 C323.00 C323.11 C323.12 C324.00 C328.00 Cyu8D00 44Q3.00	
Smoking		305.1x V15.82	137J. XE0oq Xa1dC	P17

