### 7.2. Regulatory action

In the frame of 13th PSUR assessment, data submitted raised concern regarding cardiovascular safety beyond the already recognized risk for venous thromboembolism. Analysis of pooled data from randomized studies in around 7,500 post-menopausal women with osteoporosis showed an increased risk of myocardial infarction with Protelos/Osseor as compared with placebo (1.7% versus 1.1 %), with a relative risk of 1.6 (95% CI, 1.07 to 2.38), and an increased risk of venous thrombotic and embolic events — 1.9% versus 1.3 % with a relative risk of 1.5 (95% CI, 1.04 to 2.19).

As a result of this assessment, an increased risk for serious cardiac disorders, including myocardial infarction has been identified and risk minimization measures specifically targeting this identified risk were recommended by the CHMP. These risk minimization measures included a restriction of the target population by excluding patients with established, current or past history of ischaemic heart disease, peripheral arterial disease and/or cerebrovascular disease and/or uncontrolled hypertension, and restricting the indication to severe osteoporosis in postmenopausal women at high risk for fracture to reduce the risk of vertebral and hip fractures and the treatment of severe osteoporosis in adult men at increased risk of fracture. Patients with significant risk factors for cardiovascular events (e.g. hypertension, hyperlipidaemia, diabetes mellitus and smoking) should only be treated with strontium ranelate after careful consideration. In addition, strontium ranelate therapy should only be initiated by a physician with experience in the treatment of osteoporosis. These changes were disseminated in the form of a DHPC in May 2013.

In view of this newly identified risk of serious cardiac disorders, an overall benefit/risk review under Article 20 of regulation (EC) No 726/2004 started in May 2013 and was finalized on 20 February 2014 ([EMA/112925/2014, 2014](#)). This led to a restriction of the indication to patients (postmenopausal women and men) with severe osteoporosis at high risk of fracture for whom treatment with other medicinal products approved for the treatment of osteoporosis is not possible due to, for example, contraindications or intolerance. As part of RMM, a new DHPC was disseminated in March 2014.

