##### *Cardiovascular risk factors*

- Hyperlipidemia according to coded diagnoses or the presence of a raised level of total cholesterol or LDL cholesterol in medical records at cohort entry/index date (also precautionary condition).
- Use of lipid lowering agents (ATC C10) at cohort entry/index date.
- Smoking status (if available) at cohort entry/index date (precautionary condition).
- Type 2 diabetes mellitus: based on recorded diagnosis or use of oral anti-diabetic agents (ATC A10B) (precautionary condition) at cohort entry/index date.
- History of diagnosed obesity (if body mass index is unavailable) at cohort entry/index date.
- Diagnosis of chronic kidney disease (as recorded in medical records) at cohort entry/index date.
- Diagnosis of hypertension on or before cohort entry/index date.
- Use of antihypertensive drugs in the year prior to cohort entry/index date: alpha blockers (ATC C02CA), B-blockers (ATC C07), ACE inhibitors (ATC C09A/C09B), Angiotensin II inhibitors (ATC C09C/C09D), calcium channel blockers (ATC C08C)).
- Use of low-dose aspirin (ATC B01AC06) or clopidogrel (ATC B01AC04) in the year prior to cohort entry/index date.
- Previous use of anticoagulants in the year prior to cohort entry/index date: vitamin K antagonists (ATC B01AA), heparins (ATC B01AB), direct thrombin inhibitors (ATC B01AE), direct factor Xa inhibitors (ATC B01AF).

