## Peripheral vascular disease

Term/Description	ICD10	ICD9CM	Read codes	ICPC
Peripheral Vascular Disease	I73.9	443.9, 443.81	G73y., G73z., Xa0IV, XE0VP, X203Q, Gyu74	K92
Atherosclerosis of arteries of the extremities	I70.2	440.20- 440.24 440.29		
Embolism and thrombosis of arteries of the upper extremities	I74.2	444.21		
Embolism and thrombosis of arteries of the lower extremities	I74.3	444.22	XaDtl	
Embolism and thrombosis of arteries of extremities, unspecified	I74.4	444.2		
Embolism and thrombosis of iliac artery	I74.5			
Peripheral angiopathy in diseases classified elsewhere	I79.2			
Insulin-dependent diabetes mellitus with peripheral circulatory complications *	E10.5	250.7		
Non-insulin-dependent diabetes mellitus with peripheral circulatory complications *	E11.5			
Bypass graft of the extremities *		440.3	XC0gN	
Chronic total occlusion of artery of the extremities *		440.4		
Diabetic ulcer lower extremities*		707.1		
Amputation due to diabetes*		785.4		
Embolism and thrombosis of an arm or leg artery			G742.00	
Peripheral arterial embolism and thrombosis NOS			G742z00	
H/O: Peripheral vascular disease procedure *			14NB.00	
Claudication distance			16I..00	
Percutaneous transluminal placement peripheral stent artery *			7A56600	
Diabetes mellitus with gangrene			C107.11	
Diabetes with gangrene			C107.12	
Diabetes mellitus, adult with gangrene			C107200	

Insulin dependent diabetes mellitus with gangrene			C108600	
Insulin dependent diab mell with peripheral angiopathy			C108G00	
Non-insulin dependent diabetes mellitus with gangrene			C109500	
Type II diabetes mellitus with gangrene			C109511	
Type 2 diabetes mellitus with gangrene			C109512	
Non-insulin-dependent d m with peripheral angiopathy			C109F00	
Type II diabetes mellitus with peripheral angiopathy			C109F11	
Type 2 diabetes mellitus with peripheral angiopathy			C109F12	
Type 1 diabetes mellitus with gangrene			C10E600	
Type 2 diabetes mellitus with gangrene			C10F500	
Type II diabetes mellitus with gangrene			C10F511	
Type 2 diabetes mellitus with peripheral angiopathy			C10FF00	
Type 2 diabetes mellitus with peripheral angiopathy			C10FF00	
Other peripheral vascular disease			G73..00	
Peripheral ischaemic vascular disease			G73..11	
Ischaemia of legs			G73..12	
Peripheral ischaemia			G73..13	
Peripheral gangrene			G732.00	
Gangrene of toe			G732000	
Gangrene of foot			G732100	
Gangrene of finger			G732200	
Gangrene of thumb			G732300	

Gangrene of hand			G732400	
Ischaemic foot			G733.00	

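### The diabetes covariate is limited to type 2, with an incomplete READ list, although the precaution the protocol reports is diabetes mellitus with no type stated

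*Protocol*

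**What the plan says.** Section 7.2 describes the restrictions in force since May 2013: "Patients with significant risk factors for cardiovascular events (e.g. hypertension, hyperlipidaemia, diabetes mellitus and smoking) should only be treated" with strontium ranelate (SR) after careful consideration. No type of diabetes is named.

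Section 9.3.4 lists the covariate as "Type 2 diabetes mellitus: based on recorded diagnosis or use of oral anti-diabetic agents (ATC A10B) (precautionary condition". It keeps the precautionary label but narrows the condition to type 2.

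The row for this condition in section 14.3.2 (Precautionary conditions) gives:

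- ICD-10: E11 only
- ICD-9-CM: "250 (except 250.*1 and 250.*2", plus 271.4, 357.2 and 366.41
- READ: "C10.. C101. F4640 G73y0 X00Ag X305t X30kk X40J5 Xa0IK XE11P XE15k XE2Ne"
- ICPC: T88 and T90

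The variable has two uses. Section 9.7.3.1 describes precautionary conditions in new SR and new bisphosphonate (BP) users. Sections 9.7.3.3 and 9.9 offer it to the case-control models, where a covariate is kept if it changes the estimate by 10%.

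**The concern.** A variable presented as the label precaution should identify the patients whom the precaution concerns. Here it is narrower by definition (type 2, oral agents). In READ it also appears to miss codes that the same appendix treats as type 2 diabetes. Section 9.6.6 turns every miss into a recorded absence, so nothing flags the loss.

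Two things are at stake: the SR-versus-BP table of precautionary conditions, and a confounder available to the models for myocardial infarction (MI) and cardiovascular death. A definition that behaves differently in each coding system also weakens comparison across databases.

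**Working it through.** **Definition.** Section 7.2 has diabetes mellitus; sections 9.3.4 and 14.3.2 have type 2, E11 and A10B. The peripheral vascular disease table in 14.3.2 uses E10.5 for insulin-dependent diabetes, so the authors had E10 at hand, yet the diabetes row omits it. In the ICD-10 sources, a patient coded E10 and treated with insulin alone is scored non-diabetic.

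**READ list.** The peripheral vascular disease table labels nine codes as type 2, type II or non-insulin-dependent: C109500, C109511, C109512, C109F00, C109F11, C109F12, C10F500, C10F511 and C10FF00. One of its terms is "Type 2 diabetes mellitus with peripheral angiopathy". Against the diabetes row:

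- Exact matching, whole code or first five characters: 0 of 9 found.
- C10.. read as a stem: 9 of 9 found, but C10E600, which the same table labels type 1, also enters, against the row heading.

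The protocol does not say which rule applies. Listing C101. beside C10.. suggests exact matching, since a stem would make C101. redundant.

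**A patient who stays in the comparison.** The chronic kidney disease list contains C109000 and C10F000. It does not label them, but they belong to the families labelled type 2 above. Kidney disease is not an exclusion in section 9.2.5.3. On exact matching, a THIN patient with only one of these codes and no A10B drug is kidney-disease-yes and diabetes-no in the case-control study.

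**ICD-9-CM rule.** The exclusion leaves every other fifth digit of 250 in. The protocol nowhere says what the fifth digits mean; its other uses (250.7, 250.4x) do not help. Whether the excluded pair suits a type 2 heading cannot be settled from the document.

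**Reach** (2012 incident SR users, Table (9.5) 1, total 5,819):

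- SIDIAP (ICD-10): 4,008 / 5,819 = 68.9%
- HSD (ICD-9-CM): 1,209 / 5,819 = 20.8%
- THIN (READ): 514 / 5,819 = 8.8%

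The READ question concerns 8.8% of these users, the ICD-9-CM query 20.8%, and the type 2 wording every database.

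**Size of bias.** The protocol gives no diabetes prevalence, rate ratio or code sensitivity, so these are assumptions: prevalence 10% in BP users and 8% to 15% in SR users; MI rate ratio (RR) 1.5 to 3; flag sensitivity Se of 0.7 or 0.5, specificity 1.

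- Diabetes omitted: bias = (1 + p_SR(RR−1)) / (1 + p_BP(RR−1)). At RR 3: 1.16/1.20 = 0.967 (8% v 10%) and 1.30/1.20 = 1.083 (15% v 10%).
- Flag used: replace p by q = p(1−Se)/(1−p·Se), the share of diabetics among flag-negatives. At Se 0.5, q is 0.0417, 0.0526 and 0.0811 for p of 8%, 10% and 15%. At RR 3: 1.083/1.105 = 0.980 and 1.162/1.105 = 1.051. At Se 0.7 the range is 0.987 to 1.034.
- Larger contrast the other way, 7% SR v 14% BP, RR 2 to 3: 0.977 to 0.955 at Se 0.7, and 0.964 to 0.932 at Se 0.5.
- Larger contrast upward, 20% SR v 10% BP, RR 3: 1.07 at Se 0.7 and 1.106 at Se 0.5.

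These residual factors apply among flag-negatives. With specificity 1 the flag-positive stratum is unbiased, so the pooled factor is nearer 1.

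**The 10% rule.** In the main range, omitting diabetes altogether moves the odds ratio by at most about 8%, so the variable might not enter even if perfectly coded. At 7% v 14% the shift is 6% for RR 2 (1.07/1.14 = 0.939) and 11% for RR 3 (1.14/1.28 = 0.891).

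**The case against.** The case against giving this much weight is good in several respects.

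- **The A10B limb captures anyone on an oral agent, whatever the code.** This stands. Those at risk of being missed are the remainder: type 1, and type 2 on insulin or diet alone, without a listed code.
- **The code lists are provisional** (9.6 and 14.3.2), and incidence is benchmarked by database (9.6.4). This stands for the READ and ICD-9-CM entries. It does not cover the type 2 and A10B restriction, which is in the body text of 9.3.4. A narrowing applied in every database is also unlikely to show as an outlier.
- **The bias is small beside sampling error after June 2013.** Section 9.5.2 expects 1,500 to 3,000 incident users in 2013-2015. Scaling by 25,128/31,500 = 0.798 and by 0.0019 × 2 years gives about 5 to 9 MIs in SR users. With exp(1.96/√n) on SR cases alone, that is a confidence factor of roughly 1.9 to 2.5 each way. This stands.

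A reader might also infer three stronger claims that the documents do not support:

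- **That the odds ratio is biased downward because the label steers SR away from diabetics.** The label asks for careful consideration, and no prevalence is given. Assumed values move the factor either way.
- **That the ICD-9-CM rule excludes the wrong digits.** The protocol does not define them.
- **That a patient coded C10F500 is counted as non-diabetic in the MI model.** The table lists that code under peripheral vascular disease, and peripheral arterial disease is excluded from the comparative study. The example holds only for the incidence-rate cohort, which has no exclusions (9.2.5.2).

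**Conclusion.** The mismatch is real and is shown by the protocol's own text: the precaution is diabetes mellitus, while the variable reported under that name is type 2 only. The READ row is deficient on either reading. Exact matching loses type 2 codes used elsewhere in the appendix, and stem matching admits type 1 against the heading. The ICD-9-CM exclusion is a query, not a demonstrated error.

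The weight is minor to moderate. Under the main assumptions, a flag that finds 50% to 70% of diabetics leaves a factor of 0.98 to 1.05 on the MI odds ratio; the more extreme contrasts reach about 0.93 or 1.11. All of these rest on assumed prevalences and sensitivities, the direction is not established, and the 10% rule may leave diabetes out of the model. The firmer gains from correcting it are a true report of the label precaution in the 9.7.3.1 table and one consistent definition across databases.

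**What to change.** In sections 9.3.4 and 14.3.2, replace the item by diabetes mellitus of any type, defined as any recorded diabetes code or any A10 drug including insulin. The codes would be:

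- ICD-10: E10, E11 and the other diabetes categories
- ICD-9-CM: 250 with all fifth digits
- READ: C10.. plus the C108, C109, C10E and C10F families already used in the peripheral vascular and kidney disease lists
- ICPC: the diabetes codes

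State whether READ codes match exactly or by stem. If a type 2 row is kept for description, have the HSD partner confirm the ICD-9-CM exclusion against the fifth-digit definitions.

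The cost is a one-line covariate edit and a code-list revision before extraction, when 14.3.2 already foresees discussing the lists with the partners. No new data are needed. THIN codes drugs by BNF/Multilex, so insulin must be mapped there, as the oral agents already must be.
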